10.4 Analysis of Vital Signs

Each vital sign variable will be summarized for the following time points:

- Subjects originally randomized to dupilumab in Study M16-046 and continued in Study M19-850: All post-baseline visits in M19-850. The Baseline for this group is defined as the last non-missing observation on or before their first dose of study drug in M19-850.
- Subjects originally randomized to upadacitinib in Study M16-046 and continued in Study M19-850: All post-baseline visits in M16-046 and M19-850. The Baseline for this group is defined as the last non-missing observation on or before their first dose of study drug in M16-046.

The summary includes non-missing observations, mean and standard deviation, median, minimum and maximum. Mean change from baseline to each applicable post-baseline visit mentioned above will be summarized for each vital sign variable, with the number of observations, baseline mean, and visit mean. The change from baseline mean, standard error, and 95% confidence interval will be presented for the mean change from baseline.

Vital sign variables will be evaluated based on potentially clinically important (PCI) criteria during the administration of upadacitinib in Study M16-046 and Study M19-850 (Appendix C). For each vital sign PCI criterion, the number and percentage of subjects who have a vital sign value meeting the criteria will be summarized. Listings will be provided to summarize subject-level vital sign data for subjects meeting PCI criteria.

10.5 Safety Subgroup Analyses

There are no planned subgroup analyses for safety.

10.6 Other Safety Analyses

There are no other safety analyses planned.

11.0 Other Analyses

There are no other analyses.

12.0 Interim Analyses

One interim analysis is planned for this study, which will take place after all ongoing subjects finish the Week 16 Visit with cutoff date as 09MAR2021.

12.1 Data Monitoring Committee

There is no Data Monitoring Committee for this open-label study.

13.0 Overall Type-I Error Control

14.0 Version History

[figure not shown]
Table 2.SAP Version History Summary

Version	Date	Summary
1.0	26 February 2020	Original version
2.0	09 April 2021	Added Section 8.0 following new SAP template. Section 2.2: Updated Figure of study design to incorporate the protocol amendment. Also added description about extending the study duration of certain countries and regions. Section 5.0: Removed the statement of summarizing screen failures since there will be no screening for this study. Also removed the statement of summarizing subjects with at least
		one dose of study drug. Because 'having at least one dose of study drug' is already the definition of ITT Population.
		Section 6.0: Added more categories of exposure duration following the protocol amendment of extending the dosing duration.
		Section 7.1. Removed baseline summary of Daily worst pruritus Numerical Rating Scale (NRS) as this is not applicable for M19-850 Baseline.
		Section 7.2: Clarified that Medical History will be summarized based on ITT Population.
		Section 7.3: Clarified that Prior and Concomitant Medication will be summarized based on Safety Population.
		Section 9.1 and Section 12.0: State that we would conduct an Interim Week 16 Lock.
		Section 9.2: Clarified that OC will exclude values after a subject prematurely discontinue from study +1 days.
		Section 10.3: Clarified the Baseline definition of lab analysis, as well as the visits for analysis.
		Section 10.4: Clarified the Baseline definition of vital sign analysis, as well as the visits for analysis.
		Appendix A: Added 'Subject with Deviation Related to COVID-19 Pandemic' to be consistent with M16-046.
		Appendix F: Added this section to include the activity schedule.

 Table 2.
 SAP Version History Summary (Continued)

Version	Date	Summary
3.0	14 April 2021	Section 10.2.7: Deleted 'listings of pre-treatment AE' as they are not needed for this open label extension study.
4.0	21 June 2021	Section 5.0: Clarified that subjects who were rescued in the study will not be summarized.
		Section 6.0: Clarified that study drug duration and compliance will be summarized based on Safety Population.
		Section 7.1: Modified the demographics section to be consistent with eCRF design.
		Section 7.1: Added the Worst Pruritus NRS summary for both M16-046 and M19-850 Baseline, as well as Daily NRS for M16-046 Baseline.
		Section 10.2.3: Clarified that the TEAE will be summarized by SOC and PT and maximum toxicity instead of by maximum toxicity and SOC and PT.
		Appendix C: Updated the PCI criteria to be consistent with M16-046.
5.0	01 August 2023	Section 4.0: Added statement about excluding a site from all analyses due to non-compliance.

[figure not shown]
15.0 References

Appendix A. Protocol Deviations

The number and percentage of subjects who reported at least one of the following protocol deviation categories will be provided.

[figure not shown]
- Subject entered into the study even though s/he did not satisfy entry criteria.
- Subject developed withdrawal criteria during the study and was not withdrawn.
- Subject received wrong treatment or incorrect dose of study.
- Subject took prohibited concomitant medication.
- Subject with deviation related to COVID-19 Pandemic

Appendix B. Definition of Adverse Events of Special Interest

AEs of Special Interest (AESI) will be identified by the following CMQ, SMQ, and other search criteria:

AESI	Type of MedDRA Query	Broad or Narrow Search	SMQ/CMQ Search Criteria
Serious Infections	CMQ		"Infections" – Subset for SAEs
Opportunistic Infection excluding tuberculosis and herpes zoster	CMQ		"Opportunistic Infection excluding tuberculosis and herpes zoster"
Malignancy	SMQ		"Malignant Tumours"
Non-Melanoma Skin Cancer (NMSC)	SMQ/CMQ	SMQ Broad	Skin Malignant tumours (Broad SMQ) removing Melanoma CMQ
Malignancy excluding NMSC			Malignancy Narrow SMQ and removing NMSC output
Lymphoma	SMQ		"Malignant Lymphomas"
Hepatic Disorder	SMQ	Narrow	"Drug Related Hepatic Disorders"
Adjudicated Gastrointestinal Perforations	Adjudicated events identified by the "Gastrointestinal Perforation" SMQ Narrow search		
Anemia	CMQ		"Non-Hemolytic and Non- Aplastic Anemias"
Neutropenia	CMQ		"Hematological Toxicity – Neutropenia"
Lymphopenia	CMQ		"Hematological Toxicity – Lymphopenia (Veliparib Product Specific)"
Herpes Zoster	CMQ		"Herpes Zoster"
Creatine Phosphokinase (CPK Elevation)	PT		Search only for the PT of "Blood creatine phosphokinase increased"
Renal Dysfunction	SMQ	Narrow	"Acute Renal Failure"
Active Tuberculosis	CMQ		"Active Tuberculosis"

AESI	Type of MedDRA Query	Broad or Narrow Search	SMQ/CMQ Search Criteria
Adjudicated cardiovascular events ^a	Output from CAC		
MACE*			
Cardiovascular Death			
Non-fatal Myocardial Infarction			
Non-fatal Stroke			
Other Adjudicated Cardiovascular Events			
Undetermined/Unknown Cause of Deaths			
Adjudicated Thrombotic Events	Output from CAC		
VTE**			
Deep Vein Thrombosis			
Pulmonary Embolism			
Other Venous Thrombosis	·		
Arterial Thromboembolic Events (non-cardiac, non- neurologic)			

CAC = Cardiovascular Adjudication Committee; CMQ = company MedDRA query; PT = preferred term; SMQ = standard MedDRA query

- * MACE: Major Adverse Cardiovascular Events, defined as cardiovascular death, non-fatal myocardial infarction and non-fatal stroke.
- ** VTE: Venous thromboembolic events, defined as deep vein thrombosis (DVT) and pulmonary embolism (PE) (fatal and non-fatal).
- a. Reviewed and adjudicated by an independent Cardiovascular Adjudication Committee in a blinded manner.

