3.2 Primary Safety Endpoints

- Treatment emergent adverse events (TEAEs);
- Serious adverse events (SAEs);
- Adverse events of special interest (AESI);
- AEs leading to discontinuation of study drug;
- Vital signs, laboratory tests, and physical examination findings.

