All AEs reported from the time of study drug administration through 30 days after the last dose of study drug administration will be collected, whether solicited or spontaneously reported by the subject.

Additionally, in order to assist the adjudication process, additional information on any potential major adverse cardiovascular events will be collected, if applicable.

Adverse event information will be collected as shown in Figure 2.

Figure 2. Adverse Event Collection

- * Any AEs occurring prior to the first dose of Study M19-850 should be considered as AEs for Study M16-046, regardless of when the consent form is signed.
- ** Any AEs occurring on or after the first dose of Study M19-850 should be considered as AEs for Study M19-850.

AbbVie will be responsible for Suspected Unexpected Serious Adverse Reactions (SUSAR) reporting for the Investigational Medicinal Product (IMP) in accordance with global and local requirements. A SUSAR is an adverse reaction of which the nature or severity is not consistent with the applicable product information such as investigator's brochure.

Adverse events will be monitored throughout the study to identify any of special interest that may indicate a trend or risk to subjects.

Adverse Events of Special Interest

The following AESI will be monitored during the study:

- Serious infections
- Opportunistic infections
- Herpes zoster
- Active Tuberculosis
- Malignancy (all types)
- Adjudicated Gastrointestinal perforations
- Adjudicated cardiovascular events (e.g., major adverse cardiovascular event [MACE])
- Anemia
- Neutropenia
- Lymphopenia
- Renal dysfunction
- Hepatic disorders
- Elevated CPK

- Adjudicated embolic and thrombotic events (non-cardiac, non-central nervous system).
- COVID-19 (consider while pandemic is ongoing).

Adverse Event Severity and Relationship to Study Drug

The investigators will rate the severity of each AE according to the National Cancer Institute (NCI) Common Terminology Criteria for Adverse Events (CTCAE) version 5.0.

If no grading criteria are provided for the reported event, then the event should be graded as follows:

Mild (Grade 1) Asymptomatic or mild symptoms; clinical or diagnostic observations only;

intervention not indicated

Moderate (Grade 2) Minimal, local or noninvasive intervention indicated; limiting age-

appropriate instrumental activities of daily living (ADL)

Severe (Grade 3 - 5)

Grade 3 Severe or medically significant but not immediately life-threatening;

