Supplemental study case report forms should be completed in the event of COVID-19 related missed/virtual visits, study drug interruptions or discontinuations, or adverse events (including capture of specific signs/symptoms of infection and testing results).

COVID-19 infections should be captured as adverse events. If the event meets the criteria for a serious adverse event (SAE), then follow the SAE reporting directions per the protocol and above. The following COVID-19 related supplemental eCRFs should be completed (for both serious and non-serious events):

- COVID -19 Supplemental Signs/ Symptoms
- COVID-19 Status Form

If a subject has a confirmed or suspected COVID-19 infection and study drug was interrupted, the investigator should contact the sponsor emergency medical contact listed above before reintroducing study drug.

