7.4 Statistical Analyses for Safety

Safety will be assessed by AEs, physical examination, laboratory assessments, and vital signs. Note that missing safety data will not be imputed. Analysis details will be specified in the SAP.

Adverse events will be coded using the Medical Dictionary for Regulatory Activities (MedDRA). Treatment-emergent adverse events are defined as those that began or worsened in severity after the first dose of study drug and no more than 30 days after the last dose of the study drug. The number and percentage of subjects experiencing TEAEs will be tabulated using the MedDRA SOC and PT, by severity, and by relationship to the study drug as assessed by the investigator. Summaries (including percentages and events per 100 patient-years) of SAEs, deaths, AEs leading to discontinuation, and AESI will be provided as well.

For laboratory and vital signs, mean change from Study M16-046 Baseline and percentage of subject with evaluations meeting criteria for pre-defined Potentially Clinically Significant values will be summarized.

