10.2.6 Adverse Events of Special Interest

The AESI categories will be identified by the following search criteria per Standard MedDRA Queries (SMQs)/Company MedDRA Queries (CMQs) specified in Appendix B.

Overview and exposure-adjusted event rates per 100 patient-years of Treatment-emergent Adverse events of special interest will be provided.

Treatment-emergent Adverse events of special interest will be summarized by SOC and PT and listing format. Additionally, AESI rates per 100 patient years of study drug exposure using SOC by PT will be provided for each treatment group.

Information on the extent of herpes zoster infection and acne will be summarized as collected in the respective AE form.

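### COVID-19 is on the protocol's list of adverse events of special interest but has no row in SAP Appendix B, so the special-interest outputs will carry no COVID-19 category

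*SAP*

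**What the plan says.** Protocol 3.2 includes "Adverse events of special interest (AESI)" among the primary safety endpoints, and SAP 3.1 repeats this. Protocol 6.1 then lists the events to be monitored under that name. The final entry is "COVID-19 (consider while pandemic is ongoing)". The same section states that "COVID-19 infections should be captured as adverse events" and asks for two supplemental forms for serious and non-serious events alike. On output, Protocol 7.4 says: "Summaries (including percentages and events per 100 patient-years) of SAEs, deaths, AEs leading to discontinuation, and AESI will be provided as well".

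SAP 10.2.6 states: "The AESI categories will be identified by the following search criteria per Standard MedDRA Queries (SMQs)/Company MedDRA Queries (CMQs) specified in Appendix B". It plans an overview, exposure-adjusted event rates, tables by system organ class (SOC) and preferred term (PT), and a listing. Appendix B holds the search criteria, under the opening line "AEs of Special Interest (AESI) will be identified by the following CMQ, SMQ, and other search criteria", and has no COVID-19 row. SAP 10.6 adds: "There are no other safety analyses planned". Section 11.0 plans no other analyses. SAP 1.0 says that changes from the protocol's analyses are set out in Section 14.0, which is silent on COVID-19 as an AESI.

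**The concern.** Appendix B is the working definition of a primary safety endpoint: a programmer will build the AESI tables from it. A category that the protocol names but Appendix B lacks will not be built, and nothing in the SAP shows that this was intended.

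A grouped, exposure-adjusted figure matters here because planned exposure differs between subjects. SAP 2.2 follows some countries to Week 136 and the rest to Week 52, and SAP 10.1 counts safety data from the first upadacitinib dose in either study. Crude percentages over such unequal periods are hard to read. Protocol 2.2 also says that the effect of upadacitinib on the course of COVID-19 is not well defined, so this category was not a formality.

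**Working it through.** The plan has no figure to reproduce. The check compares the two lists item by item, then looks for another route to the same output.

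**Step 1: the lists.**

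| Protocol 6.1 category | SAP Appendix B |
|---|---|
| Serious infections | Row present |
| Opportunistic infections | Row present (excludes tuberculosis and zoster, which have their own rows) |
| Herpes zoster | Row present |
| Active tuberculosis | Row present |
| Malignancy, all types | Row present, plus subdivisions |
| Adjudicated gastrointestinal perforations | Row present |
| Adjudicated cardiovascular events | Row present |
| Anemia | Row present |
| Neutropenia | Row present |
| Lymphopenia | Row present |
| Renal dysfunction | Row present |
| Hepatic disorders | Row present |
| Elevated CPK | Row present |
| Adjudicated embolic and thrombotic events | Row present |
| COVID-19 | **No row** |

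The protocol has 15 categories and 14 are mapped: 15 − 14 = 1 unmapped, COVID-19.

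**Step 2: other COVID-19 content in the SAP.** There is a protocol deviation category in Appendix A and the version-history entry that added it. Neither concerns adverse events. SAP 10.2.6 and 10.2.8 plan summaries of the herpes zoster and acne forms; no summary of the COVID-19 forms is planned.

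**Step 3: what still reaches the tables.**
- COVID-19 events are adverse events, so they enter the treatment-emergent tables by SOC and PT, severity and relationship (SAP 10.2.3).
- Serious cases, and cases leading to discontinuation or death, enter the summaries and listings of 10.2.5 and 10.2.7.
- Serious cases would also be expected in the Serious Infections row, which is the Infections query restricted to serious events. The contents of that query are not shown.
- SAP 10.2.1 mentions exposure-adjusted numbers of events but does not clearly promise them for each PT. SAP 10.2.4 names seven broad categories for rates, none of them COVID-19.

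What no section guarantees is a pre-specified COVID-19 grouping with a subject count, a rate per 100 patient-years and an AESI listing. Non-serious cases are the main gap, because the Serious Infections row cannot hold them.

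**Step 4: why the rate matters.** The Week 24 visit of Study M16-046 is Baseline here. Assuming upadacitinib was dosed throughout those 24 weeks in subjects randomized to it, the planned maximum exposures are:
- dupilumab in M16-046, Week 52 countries: 52 weeks
- upadacitinib in M16-046, Week 52 countries: 24 + 52 = 76 weeks
- dupilumab in M16-046, extended countries: 136 weeks
- upadacitinib in M16-046, extended countries: 24 + 136 = 160 weeks

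The last figure matches the top exposure category in SAP 6.0. The longest planned exposure is 160 / 52 ≈ 3.1 times the shortest.

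**The case against.** A reader might infer that COVID-19 will go unreported, or will be absent from every special-interest table. The documents do not support that: Step 3 shows several routes by which events are tabulated, and the Serious Infections row would be expected to contain the serious ones.

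The protocol entry is also the only one of the 15 with a qualifier. The word consider leaves discretion, and neither document says when the pandemic ends. The interim cutoff of 09MAR2021 in SAP 12.0, close to the protocol synopsis date of 07 January 2021, supports the condition for the interim period. It does not settle the question for follow-up to Week 136 under a SAP dated 01 August 2023.

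The versions do not match either. The supplied protocol ends treatment at Week 52, while the SAP reflects a later amendment that extended dosing in some countries. That amendment may have kept or removed COVID-19; this cannot be checked.

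It is tempting to read the COVID-19 deviation category, added in SAP version 2.0, as proof that the SAP was revised for the pandemic and this row was overlooked. Section 14.0 gives another reason for it, consistency with Study M16-046. Nor do the documents show how COVID-19 cases would spread over PTs, so the point cannot rest on fragmented coding.

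All of this stands and limits the consequence. It does not remove the discrepancy: on the supplied text the protocol names the category, the SAP has no definition for it, and no reason is recorded.

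**Conclusion.** The mismatch holds and is worth correcting. One of 15 protocol categories within a primary safety endpoint has no definition in the SAP, so the AESI overview, rates and listing will lack it. The size is moderate: the loss is a grouped count and an exposure-adjusted rate, mainly for non-serious cases. The number of cases is not given, so the effect on any table cannot be quantified. No hypothesis test depends on it, because Protocol 7.3 plans none.

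A reader might go further and infer that a pooled AESI total is understated. SAP 10.2.6 specifies no pooled total, so that does not follow.

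The conclusion assumes that COVID-19 remains on the list in the protocol version now in force, and that the pandemic condition held for at least part of the trial.

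**What to change.** Add a COVID-19 row to Appendix B with search criteria defined by the sponsor, and carry it through the 10.2.6 overview, rates per 100 patient-years and listing. Cover at least the period in which the protocol's condition held, and state how that period is set. Showing serious and non-serious cases separately would make the overlap with Serious Infections visible.

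If the current protocol no longer lists COVID-19 as an AESI, record that in Section 14.0 with the amendment that removed it; no new output is then needed.

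The cost is one row in Appendix B and one more row in outputs already planned. COVID-19 infections are already captured as adverse events, so no new data collection is required.

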Appendix C. Potentially Clinically Important Criteria for Safety Endpoints

The criteria for Potentially Clinically Important (PCI) laboratory findings are described in Table C-1 and Table C-2, and the PCI criteria for vital sign findings are described in Table C-3.

Table C-1. Criteria for Potentially Clinically Important Hematology Values

			Definition of Potentially Clinically Important
Hematology Variables	Grade	Units	Very Low
Hemoglobin	3	g/L	< 80.0
Platelets count	3	$10^{9}/L$	25.0 - < 50.0
	4	$10^{9}/L$	< 25.0
Leukocytes	3	$10^{9}/L$	1.0 - < 2.0
	4	$10^{9}/L$	< 1.0
Neutrophils	3	$10^{9}/L$	0.5 - < 1.0
	4	$10^{9}/L$	< 0.5
Lymphocytes	3	$10^{9}/L$	0.2 - < 0.5
	4	$10^{9}/L$	< 0.2

Note: A post-baseline value must be more extreme than the baseline value in CTC grade to be considered a potentially clinically important finding.

Table C-2. Criteria for Potentially Clinically Important Chemistry Values

Chemistry	emistry		Definition of Po	Definition of Potentially Clinically Important				
Variables	Grade	Units	Very Low	Very High				
ALP	3	U/L		$> 5.0 \times \text{ULN} - 20.0 \times \text{ULN}$				
	4	U/L		$> 20.0 \times ULN$				
SGOT/AST	3	U/L		$> 5.0 \times ULN - 20.0 \times ULN$				
	4	U/L		$> 20.0 \times ULN$				
SGPT/ALT	3	U/L		$> 5.0 \times \text{ULN} - 20.0 \times \text{ULN}$				
	4	U/L		$> 20.0 \times \text{ULN}$				
Albumin	3	g/L	< 20					
Glucose	3	mmol/L	1.7 - < 2.2	> 13.9 – 27.8				
	4	mmol/L	< 1.7	> 27.8				
Triglycerides	3	mmol/L		> 5.7 – 11.4				
	4	mmol/L		> 11.4				
Creatinine	3	umol/L		$> 3.0 \times ULN - 6.0 \times ULN$ or $> 3.0 \times Baseline$				
	4	mcmol/L		$> 6.0 \times ULN$				
Potassium	3	mmol/L	2.5 - < 3.0	> 6.0 – 7.0				
	4	mmol/L	< 2.5	> 7.0				
Calcium	3	mmol/L	1.5 - < 1.75	> 3.1 – 3.4				
	4	mmol/L	< 1.5	> 3.4				
Sodium	3	mmol/L	120 - < 130	155 - <160				
	4	mmol/L	< 120	> 160				
Phosphate	3	mmol/L	0.3 - < 0.6					
	4	mmol/L	< 0.3					
CPK	3	U/L		$> 5.0 \times ULN - 10.0 \times ULN$				
	4	U/L		$> 10.0 \times ULN$				
Total Cholesterol	3	mmol/L		10.34 <- 12.92				
	4	mmol/L		> 12.92				

Note: A post-baseline value must be more extreme than the baseline value with at least one CTC grade of worsening to be considered a potentially clinically important finding.

[figure not shown]

Table C-3. Criteria for Potentially Clinically Important Vital Sign Values

Vital Signs	Category	Criteria for Potential Clinically Significant Vital Signs		
Systolic Blood Pressure	Low	Value \leq 90 mmHg and decrease \geq 20 mmHg from Baseline		
	High	Value ≥ 160 mmHg and increase ≥ 20 mmHg from Baseline		
Diastolic Blood Pressure	Low Value ≤ 50 mmHg and decrease ≥ 10 mmHg from Base			
	High	Value ≥ 100 mmHg and increase ≥ 10 mmHg from Baseline		
Pulse (bpm)	Low	Value ≤ 50 bpm and decrease ≥ 15 bpm from Baseline		
	High	Value ≥ 120 bpm and increase ≥ 15 bpm from Baseline		
Weight	Low	> 7% increase from baseline		
	High	> 7% decrease from baseline		

